2.0 TRIAL DESIGN

2.1 Trial Design

This study is an open label, single arm study which will enroll patients with locally advanced squamous cell carcinomas of the larynx. Positive tumor PDL1 expression by IHC will not be required for enrollment.

All patients will receive Pembrolizumab and cisplatin in combination with radiation. Pembrolizumab 200 mg flat dose given Q21 days will begin 3 weeks prior to initiation of chemoradiation and continued through the 21-day cycle until completion of chemoradiation. Cisplatin will be given 100 mg/m² every 21 days during radiation as per standard of care.

Pembrolizumab has well defined toxicities as single agent and has non-overlapping mechanisms of action with cisplatin and radiation. The safety of these agents used in combination has not been previously described, therefore the study will begin with a safety run-in phase 1 followed by the phase II design. See statistical section for details.

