2.1.1 Phase I run in

Both drugs are FDA approved for other disease indications, with safety and tolerability well described at the approved doses. Therefore the limited phase I portion of this study aims to assess the safety and tolerability of this drug combination at their established doses along with concurrent radiation. There will be no dose escalation cohorts within this phase I run in group.

The first six patients will constitute the phase I portion of this study. These initial 6 patients will be assessed for dose limiting toxicities (DLTs, defined in Section 2.1.1.1)

from the start of study treatment until the start of cycle #2 concurrent cisplatin/radiation and pembrolizumab. After these first 6 patients initiate cycle #1, enrollment to the study will be temporarily halted, and a formal DLT evaluation of all 6 patients will be conducted.

If ≤ 2 of these six patients experience DLTs after completion of cycle #1 concurrent cisplatin/radiation and Pembrolizumab, then the study will proceed to the phase II portion, using Pembrolizumab 200mg IV Q21 days and cisplatin 100mg IV each 21 day cycle.

If > 2 of these first 6 patients experience a DLT upon completion of cycle #1, the protocol will be amended to investigate use of pembrolizumab 200 mg IV Q 21 days subsequent to completion of chemoradiation. (3-6 weeks after last dose of radiation) (upon Merck approval)

Only upon completion of the DLT evaluation for these first 6 patients and the determination of appropriate Phase II dose, will enrollment reopen for the phase II expansion.

If toxicity results are unclear, we will allow 6 additional patients into Phase I portion (6 + 6). The second cohort will be assessed based on above definitions for DLTs. Unclear toxicity can include (but not limited to) adverse effects that are considered secondary to cisplatin or radiation and per protocol are not considered DLT (see section 2.1.1.1 for definition of DLT) , however, the investigator strongly feels they could be related to study drug or exacerbated by concurrent use of study drug and chemoradiation. This investigator initiated study will be under the oversight of the University of Cincinnati IRB and Data and Safety Monitoring committee.

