5.2.1 Dose Selection/Modification

5.2.1.1 Dose Selection

The rationale for selection of doses to be used in this trial is provided in Section 4.0 – Background and Rationale.

Pembrolizumab will be dosed as a flat dose.

Details on preparation and administration of pembrolizumab (MK-3475) are provided in the Pharmacy Manual.

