5.2.1.3 Dose Modification for Cisplatin

1. Neutropenia: If on the day of scheduled treatment with cisplatin the absolute neutrophil count (ANC) is $< 1200/\text{mm}^3$, hold the second chemotherapy treatment but not the radiation until $\text{ANC} \geq 1200/\text{mm}^3$, then treat at 100% dose. Neutropenic fever (i.e. any fever $> 38.5^\circ\text{C}$ with an $\text{ANC} < 1000/\text{mm}^3$) will require a 25% dose reduction of the next cisplatin dose. If neutropenic fever occurs with both the first and second dose, cisplatin should be discontinued.
2. Thrombocytopenia: If on the day of scheduled treatment with cisplatin the platelet count is $< 75,000/\text{mm}^3$, hold chemotherapy treatment but not the radiation until platelets are $\geq 75,000/\text{mm}^3$, then treat at 100% dose. Thrombocytopenia that results in bleeding will require a 25% dose reduction of the following cisplatin dose.
3. Neurotoxicity: If grade 2 neurotoxicity develops, hold cisplatin (but continue RT) until toxicity improves to \leq grade 1, then reduce the following cisplatin dose to 80 mg/m^2 . If any signs of grade 3 or greater neurotoxicity occur, discontinue cisplatin, but continue RT.
4. Renal Adverse Events: Cisplatin dose should be based on creatinine clearance immediately prior to the second and third cisplatin dose using the following guidelines:
Note: Creatinine clearance must be calculated (Cockcroft-Gault) in order to make dose adjustment. If the calculated clearance is 50 mL/min or above, a 24-hour urine collection is not needed, but if the calculation is less than 50 mL/min , a 24-hour urine collection is mandated, and the cisplatin dose will be determined as follows:
Creatinine Clearance Cisplatin Dose
 $> 50 \text{ ml}/\text{min}$ then administer 100 mg/m^2
40-50 ml/min then administer 50 mg/m^2
 $< 40 \text{ ml}/\text{min}$ Hold drug*
*Cisplatin should be held (but the RT continued) and the creatinine measured weekly, until creatinine clearance is $> 50 \text{ ml}/\text{min}$, and then the next and following doses of cisplatin should be given at the reduced dose of 50 mg/m^2 .
5. Nausea and Vomiting: Maximum supportive therapy will be given, and cisplatin will be continued at full dose for \leq grade 2 nausea and vomiting. For grade 3 nausea and vomiting refractory to supportive therapy, cisplatin will be held until recovery to $<$ grade 2. No dose reductions will be made.

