6. Mucositis: Significant mucositis (grade 3-4, CTCAE, v. 4) is expected from radiation and cisplatin and should not be a reason for a treatment break, unless it significantly interferes with fluid intake or nutrition. Aggressive supportive care is encouraged as well as consideration of a PEG tube if not already done.
7. Ototoxicity: For clinical hearing loss not requiring a hearing aid, reduce cisplatin to 50 mg/m^2 . For hearing loss requiring a hearing aid, discontinue cisplatin. For grade 2-3 tinnitus (CTCAE, v. 4) at the time of retreatment, hold cisplatin until improvement to grade 1 or less and then reduce the following doses of cisplatin to 50 mg/m^2 . If tinnitus does not improve to grade 1 or less by the last day of

radiation therapy, discontinue cisplatin. An audiogram is recommended when there is any report of significant change in hearing and/or an increase in tinnitus.

8. Other Toxicities: For any other grade 3-4 adverse events, hold cisplatin until toxicities have recovered to grade 1 or less.

If the second or third dose of cisplatin is delayed more than 21 days because of hematologic, neurologic, renal, or other adverse events, that dose will be omitted. If a weight change of $\geq 10\%$ occurs, the following cisplatin doses should be adjusted.

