5.2.1.4 Timing of Dose Administration

Trial treatment should be administered on Day 1 of each cycle after all procedures/assessments have been completed as detailed on the Trial Flow Chart (Section 6.0). Trial treatment may be administered up to 2 days before or after the scheduled Day 1 of each cycle due to administrative reasons. Day 1 cisplatin and radiation can begin up to 7 days earlier (minimum 14 days after pembrolizumab administration) if patient and /or investigator prefer to expedite initiation of radiation.

All trial treatments will be administered on an outpatient basis.

Initiation of subsequent cycles of pembrolizumab therapy may be delayed for up to 6 weeks to allow recovery from all drug-related toxicity. If the subsequent dose of pembrolizumab is delayed more than 6 weeks because of adverse events, pembrolizumab will be discontinued. Initiation of subsequent cycles of cisplatin therapy may be delayed for up to 3 weeks to allow recovery from all drug-related toxicity. If the subsequent dose of cisplatin is delayed more than 21 days because of adverse events, that dose will be omitted. Alternately, the Investigator may choose to administer supportive care (blood product transfusions) for retreatment criteria to be met. If the recovery criteria are not met after a 6-week delay, the patient will be discontinued from study treatment unless, in the opinion of the Investigator, the patient is experiencing a clinical benefit, in which case a decision regarding continuation of treatment will be made on an individual patient basis in consultation with the Merck medical monitor. Justification will be recorded in the source documents.

In the setting of dose delays, neither cisplatin nor pembrolizumab will be administered following completion of radiation therapy.

When initiating a subsequent cycle, a minimum interval of 21 days should be observed between pembrolizumab administrations and between cisplatin administrations.

Cisplatin or pembrolizumab can be given either before or after the radiation therapy fraction that is given on the same day. If radiation is held for more than 2 days (for any reason), cisplatin may be held as well until radiation resumes.

Note: pembrolizumab or cisplatin given within 48 hours of days 1 and 22 and 43 due to holidays, for example, is acceptable). Weekends count as days. Use the actual body weight for all patients. There should be no dose modifications because of obesity.

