6.0 TRIAL FLOW CHART

6.1 Study Flow Chart

Trial Period:	Screening Phase	Treatment Cycles				End of Treatment		Post-Treatment	Post Progression or new anti-cancer Therapy
						Discon	Safety Follow-up		
Treatment cycle/Title:	Main Study Screening Visit	C1 D-21	C1 D1	C1 D2 2	C1 D43	At time of Discon	30 days post discon	Every 12 weeks(± 1 w)	Every 12 weeks (±1 w)
Scheduling Window (Days):	-28 to -1	- 21 to - 14	± 2	± 2	± 2				
Informed Consent	x								
Inclusion/Exclusion Criteria	x								
Standard Chemotherapy Administered Cisplatin-100 mg			x	x	x				
Trial Treatment Administration Pembrolizumab 200 mg		x	x €	x €	x €				
Radiation- 70Gy/35 fx			x Δ	x Δ	x Δ				
Survival Status								x	x [∞]
Review Adverse Events		x	x	x	x	x	x	x €	

Trial Period:	Screening Phase	Treatment Cycles				End of Treatment		Post-Treatm ent	Post Progression or new anti-cancer Therapy
						Discon	Safety Follow-up	Follow-Up	Survival Follow-Up Phase
Treatment cycle/Title:	Main Study Screening Visit	C1 D-21	C1 D1	C1 D2 2	C1 D43	At time of Discon	30 days post discon	Every 12 weeks(± 1 w)	Every 12 weeks (±1 w)
Scheduling Window (Days):	-28 to -1	- 21 to - 14	± 2	± 2	± 2				
Directed Physical Examination		X	X	X	X	X		x¥	
Full Physical Exam	X								
Review of Concomitant Medications	X	X	X	X	X	X	X	X	
Review Medical History	X								
Subsequent Anti-Cancer Therapy Status							X		
Endoscopic Examination in Office	xç		xç					x£	
Vital Signs and Weight	x	x	x	x	x	x			
Review Speech/swallow questionnaire ç	x							x¥	
Review Nutrition questionnaire ç	x							x¥	

Trial Period:	Screening Phase	Treatment Cycles				End of Treatment		Post-Treatment Follow-Up	Post Progression or new anti-cancer Therapy
						Discon	Safety Follow-up		
Treatment cycle/Title:	Main Study Screening Visit	C1 D-21	C1 D1	C1 D2 2	C1 D43	At time of Discon	30 days post discon	Every 12 weeks(± 1 w)	Survival Follow-Up Phase Every 12 weeks (±1 w)
Scheduling Window (Days):	-28 to -1	-21 to -14	± 2	± 2	± 2				
ECOG Performance Status	x	x	x	x	x	x			
Functional Oral Intake ϕ	X							x \neq	
Pregnancy Test – Urine or Serum b-HCG if appropriate	x								
CBC with Differential	x	x	x	x	x				
Comprehensive Serum Chemistry Panel	x	x	x	x	x				
T3, FT4 and TSH	x		x		x				
Tumor Imaging (PET preferred)	x							x \neq	
Archival or Newly Obtained Tissue Collection	x		x ϕ						

Trial Period:	Screening Phase	Treatment Cycles				End of Treatment		Post-Treatment	Post Progression or new anti-cancer Therapy
						Discon	Safety Follow-up		

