7.2.1 Definition of an Overdose for This Protocol and Reporting of Overdose to the Sponsor and to Merck

For purposes of this trial, an overdose of pembrolizumab will be defined as any dose of 1,000 mg or greater (≥ 5 times the indicated dose). No specific information is available on the treatment of overdose of pembrolizumab. Appropriate supportive treatment should be provided if clinically indicated. In the event of overdose, the subject should be observed closely for signs of toxicity. Appropriate supportive treatment should be provided if clinically indicated.

If an adverse event(s) is associated with (“results from”) the overdose of a Merck product, the adverse event(s) is reported as a serious adverse event, even if no other seriousness criteria are met.

If a dose of Merck’s product meeting the protocol definition of overdose is taken without any associated clinical symptoms or abnormal laboratory results, the overdose is reported as a non-serious Event of Clinical Interest (ECI), using the terminology “accidental or intentional overdose without adverse effect.”

All reports of overdose with and without an adverse event must be reported within 24 hours to the Sponsor and within 2 working days hours to Merck Global Safety. (Attn: Worldwide Product Safety; [contact])

An overdose for cisplatin will be defined as any dose of study drug that is 10% or more over the prescribed dose per cycle as described in the study protocol. There is no specific antidote for cisplatin overdose. In the event of overdose, subsequent dose of cisplatin should be held unless approved by study Sponsor and Merck. Patient should be observed closely for signs of toxicity. As clinically indicated, appropriate supportive treatment should be provided, if applicable.

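### Cisplatin is written both as 100 mg and as 100 mg/m², including in the rule that sets the phase II regimen, and nothing says which governs

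*Combined protocol and SAP*

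**What the plan says.** All references are to the combined protocol and SAP.

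**Without a per-m² unit**
- Section 2.1.1, in the rule that applies when at most 2 of the first 6 patients have a dose-limiting toxicity: the study goes on to phase II "using Pembrolizumab 200mg IV Q21 days and cisplatin 100mg IV each 21 day cycle".
- Section 6.1, the treatment row of the flow chart: "Standard Chemotherapy Administered Cisplatin-100 mg".

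**With a per-m² unit**
- Section 2.1: "Cisplatin will be given 100 mg/m² every 21 days during radiation as per standard of care".
- Section 5.2, Table 2, which is introduced as the outline of trial treatment: 100 mg/m² every 3 weeks, at most 3 doses.
- Section 5.2.1.3, the renal table, for creatinine clearance above 50 mL/min: "then administer 100 mg/m" (the unit is per square metre).

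**Rules that depend on the dose**
- Section 5.2.1.3 sets reduced levels of 80 and 50 mg/m². It also says that after a weight change of at least 10% "the following cisplatin doses should be adjusted".
- Section 5.2.1.4: "Use the actual body weight for all patients".
- Section 7.2.1: "An overdose for cisplatin will be defined as any dose of study drug that is 10% or more over the prescribed dose per cycle", where the reference is the dose the protocol describes. The next dose is then held unless the sponsor and the drug supplier approve it.

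Pembrolizumab is the only drug expressly described as flat-dosed. Section 5.2.1.1 states: "Pembrolizumab will be dosed as a flat dose".

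**The concern.** The sentence in 2.1.1 is not background. It takes the trial from the run-in to the expansion, and 2.1.2 treats the cisplatin dose as settled at that point, before a further 41 patients enter. The flow chart is a page that sites consult at each visit. In both places cisplatin stands next to pembrolizumab 200 mg, which really is a flat dose, so a reader may take the two figures the same way.

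What is at stake is first the clarity of a cytotoxic dose. Second, the overdose definition and the dose reductions have meaning only relative to a starting dose, so an ambiguity in that dose passes into both. Third, 2.1.2 pools the whole cohort for safety and efficacy, which presumes that all patients were treated under one regimen.

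**Working it through.** The plan states no figure to reproduce here. The check is a comparison of the passages plus short arithmetic.

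**Inputs from the documents:** 100 mg (2.1.1, 6.1); 100 mg/m² (2.1, Table 2, 5.2.1.3); reduced levels of 80 and 50 mg/m² (5.2.1.3); overdose margin of 10% (7.2.1).

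**Assumption, not in the documents:** body surface area (BSA) of 1.6 to 2.1 m², as an illustrative adult range.

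**1. Where the two expressions agree.** 100 × BSA = 100 gives BSA = 1.0 m² only.

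**2. Size of the gap.** Shortfall of 100 mg against 100 mg/m² = 1 − 100/(100 × BSA). Excess of 100 mg/m² over 100 mg = BSA − 1.

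| BSA (m²) | 100 mg/m² in mg | Shortfall of 100 mg | Excess of 100 mg/m² |
|---|---|---|---|
| 1.6 | 160 | 1 − 100/160 = 37.5% | 60% |
| 2.1 | 210 | 1 − 100/210 = 52.4% | 110% |

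**3. Overdose definition.** Read against 100 mg, the threshold is 1.10 × 100 = 110 mg. A 100 mg/m² dose reaches it when 100 × BSA ≥ 110, that is, at BSA ≥ 1.1 m². The whole assumed range lies above this.

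**4. Dose reductions.** Read against 100 mg:
- The 80 mg/m² level exceeds the starting dose when 80 × BSA > 100, that is, above 1.25 m². Over the assumed range it is 128 to 168 mg.
- The 50 mg/m² level equals the starting dose at 100/50 = 2.0 m². Over the assumed range it is 80 to 105 mg.

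The reduced levels therefore do not work as reductions against a 100 mg start. The 25% reductions in 5.2.1.3 are relative to the dose, so they show no such reversal.

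**5. Effect on the design figures.** Section 8.1 bases 47 patients on 70% against 85% laryngectomy-free survival at 18 months, one-sided 10% significance, 80% power, 18 months of accrual and 6 months of further follow-up. The cisplatin dose does not enter this calculation.

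**The case against.** The strongest reply is that this is a unit dropped in drafting. No passage calls cisplatin a flat dose. Section 2.1.1 itself says that the drugs are tested at established doses and that there are no escalation cohorts. Every reduced level stated in milligrams is per m², doses follow weight change, and actual body weight is used. Table 2 is the passage that sets out to define treatment, while the flow chart is described as a summary of procedures and is cited for timing. In the text version of the document the chart is also badly broken up, so a unit lost from that row cannot be wholly excluded. Most of this stands: the context is compatible with a dropped unit. But 2.1.1 is running prose, so the table problem does not reach it, and no text tells a site which expression prevails.

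Four stronger readings are tempting and are not supported:
- **That the protocol sets a second, flat cisplatin regimen, or changes the dose for the expansion.** Two places omit the unit; none states such a regimen or such a change.
- **That the 70% benchmark becomes inapplicable.** Section 2.1 does link 100 mg/m² to standard of care, so one could argue that comparability would suffer under a different dose. But 8.1 attaches no cisplatin dose to the 70%, the background account of the cited trials gives none, and no effect on laryngectomy-free survival is quantified.
- **That a Table 2 dose would automatically stop the next one.** This needs a site to dose by one expression and judge overdose by the other, and 7.2.1 lets the sponsor and the drug supplier approve continuation.
- **That the documents settle which passages are wrong.** They do not, and that decision belongs to the sponsor.

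**Conclusion.** The inconsistency is real and lies in operative text: two places give 100 mg, three give 100 mg/m², and nothing ranks them. For an assumed BSA of 1.6 to 2.1 m² the gap is about 38% to 52% of the per-m² dose. That measures the distance between two readings of the protocol; it does not predict how patients will be dosed. The thresholds of 1.1 m² (overdose) and 1.25 m² (80 mg/m² becoming an increase) need no BSA assumption, but they apply only if 100 mg is taken as the reference dose. The sample size, significance level and power do not change. The point must be corrected because it concerns a dose in the rule that sets the phase II regimen, and clarity there costs little. It does not rest on any demonstrated bias in the primary analysis.

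**What to change.** By amendment, the sponsor should reconcile sections 2.1, 2.1.1, 5.2 (Table 2), 5.2.1.3 and 6.1 so that a single cisplatin dose and unit appears throughout. The sponsor should also confirm that the overdose definition in 7.2.1 and the reductions in 5.2.1.3 are read against that dose. Section 7.2.1 already refers to the protocol's prescribed dose, so it may need no new wording once the other passages agree. This review does not say which dose is right.

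The cost is a wording change and the IRB approval that section 10.5 requires before any change takes effect. No patients, assessments or analyses are added.

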2.1.1.1 Definition of Dose-Limiting Toxicities

All toxicities will be graded using National Cancer Institute (NCI) CTCAE Version 4.0 (see Appendix).

Dose limiting toxicity (DLT) is defined as the appearance of side effects during treatment that are severe enough to prevent continuation of planned treatment. Dose limiting toxicity is defined as grade 3 or 4 non-hematologic toxicities that is definitely, probably, or possibly related to study drug, excluding alopecia, nausea or vomiting, grade 3 tumor flare, rash, mucositis, radiation dermatitis, need for feeding tube, and grade 3 immune-related events that resolve to grade 1 or less within 28 days. However, Grade ≥ 3 immune-mediated adverse events that include pneumonitis, renal failure nephritis, and elevation of AST, ALT, or bilirubin (with an exception for patients with liver metastases with baseline Grade 2 AST or ALT) should result in discontinuation of pembrolizumab and will be considered DLT (please see Table 3 for details on dose modification) .

In addition, adverse effects that are considered secondary to cisplatin or radiation are not considered DLT (see sections 5.2.1.3 and 5.2.2.7) unless they develop after first dose of pembrolizumab and prior to initiation of cisplatin and radiation. Cisplatin or radiation adverse effects include (but are not limited to):

- Grade 3 or 4 renal impairment (with the exception of renal failure or nephritis determined to be immune-related, which will be considered a DLT).
- Grade 2-4 neurotoxicity including ototoxicity (with the exception of myasthenia gravis and Guillain-Barre syndrome, which will be considered a DLT).
- Grade 3 or 4 mucositis
- Grade 3 or 4 myelosuppression

Although the above should result in dose modifications or delays as stated in section 5.2.1.3, they will NOT be considered DLTs for pembrolizumab on this study, and will NOT interfere with expansion to phase II portion of study.

If a patient is taken off study due to the above and has not yet reached evaluation for toxicity attributed to pembrolizumab, that subject will be replaced with another patient on study.

Non hematologic toxicities that will be attributed to pembrolizumab include:

- Grade 3-4 Pneumonitis
- Grade 3-4 diarrhea/colitis
- Grade 3-4 hyperglycemia
- Grade 3-4 hypophysitis
- Grade 3-4 thyroid dysfunction (hypothyroid or hyperthyroid)
- Grade 3-4 hepatic failure (elevation of AST, ALT, Bilirubin)
- Grade 5 toxicity

Any additional grade 3-4 non hematologic toxicity that is judged by the investigator to be possibly, probably or definitely related to study drug administration will be reviewed by study monitor and PI on an individual basis.

Management and dose modifications associated with the above adverse events are outlined in Sections 5.2.1.2 and 5.6.

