Pneumonitis	2	Toxicity resolves to Grade 0-1	Toxicity does not resolve within 6 weeks of last dose or inability to reduce corticosteroid to 10 mg or less of prednisone or equivalent per day within 6 weeks.
	3-4	Permanently discontinue	Permanently discontinue
Renal Failure or Nephritis	2	Toxicity resolves to Grade 0-1	Toxicity does not resolve within 6 weeks of last dose or inability to reduce corticosteroid to 10 mg or less of prednisone or equivalent per day within 6 weeks.
	3-4	Permanently discontinue	Permanently discontinue
All Other Drug-Related Toxicity ²	3 or Severe	Toxicity resolves to Grade 0-1	Toxicity does not resolve within 6 weeks of last dose or inability to reduce corticosteroid to 10 mg or less of prednisone or equivalent per day within 6 weeks.
	4	Permanently discontinue	Permanently discontinue

Note: Permanently discontinue for any severe or Grade 3 drug-related AE that recurs or any life-threatening event.

¹ For patients with liver metastasis who begin treatment with Grade 2 AST or ALT, if AST or ALT increases by greater than or equal to 50% relative to baseline and lasts for at least 1 week then patients should be discontinued.

² Patients with intolerable or persistent Grade 2 drug-related AE may hold study medication at physician discretion. Permanently discontinue study drug for persistent Grade 2 adverse reactions for which treatment with study drug has been held, that do not recover to Grade 0-1 within 6 weeks of the last dose.

Dosing interruptions are permitted in the case of medical / surgical events or logistical reasons not related to study therapy (e.g., elective surgery, unrelated medical events, patient vacation, and/or holidays). Subjects should be placed back on study therapy within 3 weeks of the scheduled interruption, unless otherwise discussed with the Sponsor. The reason for interruption should be documented in the patient's study record.

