8.2 Statistical Analysis Plan

Safety run-in phase: Although PD-1 inhibition is not expected to increase the toxicity of chemoradiation therapy, clinical trials of pembrolizumab combined with cisplatin and radiation for locally advanced head and neck carcinoma have not been conducted. In order to protect against unexpected problems a run-in safety analysis will be performed prior to completing the rest of the first stage of study. This safety analysis will occur after 6 analyzable patients are entered into study. Pembrolizumab will be administered initially at the recommended phase II dose of 200 mg q 3 weeks. If more than 2 dose-limiting toxicities (DLTs) in the cohort of 6 patients then pembrolizumab will be given subsequent to completion of chemoradiation. In the event of 0-2 DLT events, the study will proceed as planned. A DLT will be defined as a \geq grade 3 (CTCAE, v.4) adverse event that is definitely, probably, or possibly related to study drug, excluding grade 3 tumor flare and toxicities that are strongly associated with concurrent radiation and cisplatin (for example rash, mucositis, radiation dermatitis).

LFS will be estimated using the Kaplan-Meier method. The point estimate and standard error will be obtained from the Kaplan-Meier curve and a 95% confidence interval will be calculated to estimate 18-month LFS. A z-test will be used to test the primary hypothesis of improvement in 18- month LFS from 70% to 85%.

One-year LFS, Progression-free survival, overall survival, event-free survival, and patterns of failure will be estimated using the Kaplan-Meier method. Complete response at 3 months will be estimated with an exact 95% confidence interval. For correlative studies, prognostic factors for complete response will be identified using logistic regression analysis. Prognostic factors for outcomes will be identified using Cox proportional hazards analysis.

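### The DLT definition excludes rash without a grade or cause, so on its literal terms a grade 4 pembrolizumab rash that ends the drug would not count in the six-patient run-in

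*Combined protocol and SAP*

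**What the plan says.** Section 2.1.1.1 opens by describing a DLT as a side effect "severe enough to prevent continuation of planned treatment". It then gives the working definition: grade 3 or 4, non-hematologic, at least possibly due to study drug, "excluding alopecia, nausea or vomiting, grade 3 tumor flare, rash, mucositis, radiation dermatitis, need for feeding tube", and also excluding "grade 3 immune-related events that resolve to grade 1 or less within 28 days". Pneumonitis, renal events and liver-test elevations of grade 3 or more are then restored as DLTs. Rash is not restored, and it is not on the later list of toxicities attributed to pembrolizumab.

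A separate paragraph removes effects considered secondary to cisplatin or radiation, "unless they develop after first dose of pembrolizumab and prior to initiation of cisplatin and radiation". Its examples are open-ended ("Cisplatin or radiation adverse effects include (but are not limited to") and do not name rash.

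Section 8.2 restates the definition more briefly, "excluding grade 3 tumor flare and toxicities that are strongly associated with concurrent radiation and cisplatin (for example rash, mucositis, radiation dermatitis". It has neither the 28-day item nor the exception for the pembrolizumab-only lead-in.

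Table 3 (section 5.2.1.2) has no row for rash, so a drug-related rash falls under "All Other Drug-Related Toxicity": grade 3 holds pembrolizumab and grade 4 ends it. The note to the table adds: "Permanently discontinue for any severe or Grade 3 drug-related AE that recurs or any life-threatening event".

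Under section 2.1.1, two or fewer patients with a DLT among the first six lets the study proceed. More than two leads to an amendment that moves pembrolizumab to after chemoradiation.

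**The concern.** The exclusion acts on events already judged at least possibly related to study drug, so attribution to pembrolizumab does not by itself bring a rash back into the count. Tumor flare and immune-related events carry a grade limit in the same sentence, and rash does not. An evaluator who follows the words would leave out a grade 4 rash that had just ended pembrolizumab.

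The run-in exists because section 2.1 says the safety of the combination has not been described before. Its count in six patients decides whether 41 more are enrolled on the concurrent schedule. The rule should be settled before an event occurs, particularly in an open-label trial.

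**Working it through.** **Text check for a grade 4 pembrolizumab-related rash**

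| Text | Result |
|---|---|
| 2.1.1.1, opening sentence | DLT: planned pembrolizumab cannot continue |
| 2.1.1.1, exclusion list, read literally | Not a DLT: rash has no grade or cause |
| 2.1.1.1, immune-related item | Excuses grade 3 only, which implies grade 4 counts if the rash is treated as immune-related |
| 8.2, by name | Not a DLT |
| 8.2, by its stated reason | Counts, if the rash is not a chemoradiation toxicity |
| Table 3 | Pembrolizumab permanently stopped; silent on DLT status |

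The words grade 3 before tumor flare cannot be carried forward to rash. Section 8.2 attaches them to tumor flare alone, and the immune-related item in 2.1.1.1 repeats them for itself.

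**Size**

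The plan states no figure on this point, so there is none to reproduce. The documents give no rates for rash or for other DLTs, and both are assumed below.

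- n = 6 and the threshold of more than 2 come from section 2.1.1.
- q is the assumed share of patients with another DLT: 10%, 20% or 30%.
- r is the assumed share with newly counted rash: 1% or 2%. It covers study-drug-related rash of grade 4, and of grade 3 not back to grade 1 or less within 28 days.
- Rash and other DLTs are taken as independent.

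The chance that a patient has a counted DLT is p = 1 − (1 − q)(1 − r). The chance of crossing the threshold is P(>2 of 6) = 1 − BinomCDF(2; 6, p). For q = 20% and r = 2%, p = 1 − 0.80 × 0.98 = 0.216 and P = 0.1195.

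| q | r = 0 | r = 1% | r = 2% | Rise (points) |
|---|---|---|---|---|
| 10% | 0.016 | 0.020 | 0.025 | 0.4 to 0.9 |
| 20% | 0.099 | 0.109 | 0.120 | 1.0 to 2.1 |
| 30% | 0.256 | 0.269 | 0.282 | 1.3 to 2.6 |

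At least one of the six has such a rash with probability 1 − (1 − r)^6, which is 5.9% at r = 1% and 11.4% at r = 2%. If exactly two patients already have another DLT, counting rash changes the decision with probability 1 − (1 − r)^4, which is 3.9% or 7.8%.

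These are upper figures for the stated r, because they assume that no such rash is counted now and that no discretionary safeguard acts. They also mix grade 4 with unresolved grade 3 rash; the documents offer no basis for a grade-4-only figure, which would be smaller.

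**The case against.** The best defence is that the literal reading takes one word out of context. In 2.1.1.1 rash stands beside mucositis, radiation dermatitis and feeding-tube need, all expected from chemoradiation, and 8.2 gives that association as its reason. With the opening sentence and the 28-day item, a fair reader could conclude that a grade 4 immune rash counts. This stands as evidence of intent, and it lowers the weight of the point. It does not settle the matter, because no sentence says which item governs.

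There are also safeguards. Section 2.1.1.1 ends by sending additional related grade 3–4 non-hematologic toxicity to individual review. Section 2.1.1 allows six more patients when toxicity is unclear, including events that are not DLTs by definition but that the investigator strongly suspects are drug-related. Section 5.10 permits early termination for the severity of adverse reactions, and sections 10.5 and 10.6 provide for board monitoring and weekly review. These are real, but they are discretionary. None says that such a rash is a DLT, and a second cohort would be scored on the same definitions.

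Three stronger inferences are not supported:

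- A reader might infer that the affected patient is left unprotected. Table 3 stops the drug whatever the DLT label.
- A reader might infer that every drug stop should be a DLT. Section 5.9 lets a patient with a DLT continue on modified doses, so the plan does not equate the two. The conflict lies within 2.1.1.1.
- A reader might infer that rash in the pembrolizumab-only lead-in is plainly excluded, or plainly counted. It is excluded by name in both sections. Yet 8.2's reason cannot apply before cisplatin and radiation start, and the open-ended lead-in exception in 2.1.1.1 could take rash in without naming it. The texts leave this open.

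**Conclusion.** The point holds as a minor wording error. Followed literally, 2.1.1.1 leaves out of the DLT count a grade 4 study-drug-related rash that permanently ends pembrolizumab, contrary to its own opening sentence. The context suggests that this was not meant, but nothing in the documents states the opposite.

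The effect is confined to the six-patient run-in: about 0.4 to 2.6 percentage points on the chance of crossing the threshold, resting wholly on the assumed rates and independence. It does not touch the primary analysis of 18-month laryngectomy-free survival or the sample size of 47. Whether a grade 3 lead-in rash that resolves within 28 days should count is a choice for the sponsor and is not part of the error.

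**What to change.** In both 2.1.1.1 and 8.2:

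1. Limit the rash exclusion to rash attributed to cisplatin or radiation that starts after chemoradiation begins.
2. Count as a DLT any grade 4 rash at least possibly related to pembrolizumab, including when chemoradiation may also contribute. This supplies the tie-break for a rash with two plausible causes.
3. Handle grade 3 rash judged immune-related under the existing 28-day rule of 2.1.1.1. The sponsor should state whether a grade 3 lead-in rash that resolves in that time counts.
4. Have 8.2 refer to 2.1.1.1 for these rules, since it lacks the 28-day item.

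The cost is a few words and a cross-reference. No new time limit, procedure or patient is needed. The run-in becomes slightly less permissive, by the amounts shown above, and crossing the threshold would still lead to the amendment already described in section 2.1.1.
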